8.5.2 Reporting SAEs to Health Authorities

After the SAE has been reported by the site investigator and assessed by the IND sponsor (DAIT/NIAID Medical Monitor, and the DAIT/NIAID Office of Regulatory Affairs), the IND sponsor, must report the event to the FDA using one of these two options:

- **Standard reporting (report in the IND annual report).** This option applies if the AE is classified as one of the following:
 - Serious, expected, suspected adverse reactions described in Sections [8.2.1](#), [8.2.4](#), and [8.2.5](#).
 - Serious and not a suspected adverse reaction described in Sections [8.2.1](#), [8.2.4](#), and [8.2.5](#).
- **Expedited reporting is required.** This option applies if the AE is classified as one of the following:
 - Serious and unexpected suspected adverse reactions described in Sections [8.2.1](#), [8.2.4](#), and [8.2.5](#).
 - The sponsor must report any suspected adverse reaction that is both serious and unexpected. The sponsor must report an adverse event as a suspected adverse reaction only if there is evidence to suggest a causal relationship between the study drug and the adverse event, such as:
 - A single occurrence of an event that is uncommon and known to be strongly associated with drug exposure. (e.g., angioedema, hepatic injury, or Stevens-Johnson Syndrome);
 - One or more occurrences of an event that is not commonly associated with drug exposure, but is otherwise uncommon in the population exposed to the drug (e.g., tendon rupture);
 - An aggregate analysis of specific adverse events observed in a clinical trial (such as known consequences of the underlying disease or condition under investigation or other events that commonly occur in the study population independent of drug therapy) that indicates those events occur more frequently in the drug treatment group than in a concurrent or historical control group.
 - Any findings from clinical or epidemiological studies, analysis of data pooled across multiple studies, published or unpublished scientific papers, or from animal or in vitro testing that would result in a safety-related change in the protocol, informed consent, General Investigational Plan section of the IND or other aspects of the overall conduct of the trial.

Safety reports must be submitted by DAIT/NIAID to the FDA within 15 calendar days; fatal or immediately life-threatening, serious, unexpected, suspected adverse reactions must be reported within 7 calendar days.

All site investigators must report SAEs to their respective IRBs as mandated by them.

8.5.3 Reporting SAEs to the DSMB

The DAIT/NIAID will provide the DSMB with data of all SAEs on an ongoing basis as determined by the DAIT/NIAID Medical Monitor, including expedited reporting of SAEs that are also reported to the FDA (see [Section 8.5.2](#)), and annual safety reviews of all SAEs and as indicated in [Section 3.4.1](#).

8.5.4 Reporting SAEs to IRB/EC

The DAIT/NIAID will notify all investigators of AE information. The investigator will ensure the timely dissemination of all AE information, including expedited reports, to the IRB/EC in accordance with all applicable regulations. All site investigators must report SAEs to their respective IRBs as mandated by their local IRB.

9. STATISTICAL CONSIDERATIONS AND ANALYTICAL PLAN

9.1 ANALYSIS SAMPLES

- Intent-to-treat (ITT) sample: All subjects who are randomly assigned to treatment or placebo will comprise the ITT sample.
- Per-protocol sample for the primary endpoint: All ITT subjects who are also study-compliant through the maintenance phase and have an evaluable blinded OFC at the end of the maintenance phase. Compliance is defined as completion of the maintenance phase as described in [Section 6.7.4](#); than 3 occasions on which more than 3 consecutive home doses of study medication were missed; and less than 3 non-protocol specified ingestions of peanut-containing food within a year.
- Per-protocol sample for the secondary endpoint: All participants included in the per protocol sample for the primary endpoint who are compliant with peanut avoidance during the avoidance phase and have an evaluable blinded OFC at the end of the avoidance phase. Compliance is defined as completion of the avoidance phase as described in [Section 6.7.5](#) and less than 3 non-protocol specified ingestions of peanut-containing food within a year.
- As-treated sample: All evaluable subjects, analyzed according to the amount of peanut therapy received, regardless of their randomized assignment.
- Safety sample: All enrolled subjects who receive at least one dose of OIT or placebo. Participants in the safety sample will be analyzed according to the treatment they actually received, regardless of their randomized assignment.

9.2 ANALYSIS OF ENDPOINTS

9.2.1 Overview

Analysis of study data will be conducted to address all objectives of the trial and other interrelationships among all data elements of interest to the investigators and of relevance to the objectives of the study. Analyses of the primary and secondary endpoints will be conducted using the ITT sample described above. Additional analyses using the per-protocol and as-treated samples will serve to complement the main analysis by providing more homogeneous samples with respect to actual peanut consumption and allowing a close examination of the efficacy and mechanistic characteristics of peanut OIT. Subgroup and sensitivity analyses of primary interest will be specified *a priori* and in detail within the statistical analysis plan (SAP). All statistical tests will be two-sided at the $\alpha = 0.05$ level of significance.

9.2.2 Primary Endpoint

The primary endpoint is the proportion of participants desensitized to peanut after 134 weeks OIT. The definition of desensitization is in Section [3.3.1](#). Any randomized subject without an evaluable blinded OFC will be considered a treatment failure. The proportion of participants desensitized to peanut will be compared between arms using a multivariate logistic regression model with site, peanut specific IgE, and age as covariates in the model.

In a secondary analysis, the interaction between each covariate and the treatment effect will be investigated. If no interaction is present, only the main effects and adjusted proportions and confidence intervals will be reported. Unadjusted proportions and odds ratios will also be presented with confidence intervals. All statistical analyses will be performed on each study sample specified in Section [9.1](#).

9.2.3 Secondary Endpoints

9.2.3.1 Efficacy

1. Tolerance Endpoint

This is the proportion of participants who pass the blinded OFC to 10 g peanut flour (5 g peanut protein) at week 160.

The comparison of tolerance between the two randomized groups will be performed using a multivariate logistic regression model. The statistical methods specified for the primary endpoint in [Section 9.2.1](#) and [9.2.2](#) will also be used for this endpoint.

2. Transient Desensitization Endpoint

This is the change in proportion of participants who pass the blinded OFC to 10 g peanut flour (5 gram peanut protein) at week 134 and 160. This matched, pre/post peanut avoidance comparison allows for the exploration of mechanistic and immunologic differences between children who appear to be transiently desensitized compared to those who appear to be tolerant after 26 weeks of avoidance. If there is a statistically significant increase in the rate of peanut allergy from weeks 134 and 160, this will be interpreted as evidence of transient desensitization. This within-group, paired comparison of proportions will be performed using a McNemar's test at a 0.05 level of significance within the treatment arms of both the ITT and PP analysis samples.

3. Highest Tolerated Cumulative Dose Endpoint

The highest tolerated dose of peanut protein during each blinded OFC will be analyzed within and between both placebo and peanut OIT groups. This will allow the investigation of desensitization at 134 weeks, tolerance at 160 weeks, and possible changes between week 134 and week 160. Each of these analyses will be performed in a similar manner as all other endpoint analyses. However, instead of a binary (pass or fail) blinded OFC outcome, the highest dose of peanut protein tolerated for each subject will be analyzed as a continuous outcome. Depending on the distribution of the data, parametric or non-parametric statistical methods may be performed. For example, a multivariate linear model could be used to test for desensitization at 134 weeks and tolerance at 160 weeks. A paired t-test could be used to test transient desensitization between 134 weeks and 160 weeks within the peanut OIT or placebo groups.

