allergy. This is to allow children who might still react to a challenge dose to build-up to and continue maintenance. We propose a target maintenance dose that previous experience suggests is close to the maximum that is practical to give as peanut flour (or placebo) added to other food.

The optimal duration of OIT is unknown. Previous studies indicate that one year or more of OIT results in desensitization. Results emerging in 2012 from studies with other food allergens, however, indicate that desensitization may not be long-lasting after OIT. These data indicate that when OIT is continued for up to two years the likelihood of more long-lasting tolerance is higher.

The study aims to assess both desensitization and tolerance. The assessment of tolerance, which for this study is described as the ability to tolerate oral peanut after a specified period of desensitization followed by avoidance, is a key study goal. However, the likelihood and magnitude of the tolerance effect are unknown, whereas there are good preliminary data to indicate that desensitization is a reasonable goal to test. We therefore compromised by focusing the primary endpoint on desensitization but choosing a sample size to provide a chance of seeing a tolerance effect if at least a moderate one exists.

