3.3.2 Secondary Endpoints

Efficacy:

1. Tolerance Endpoint
The proportion of participants who pass both the blinded OFC to 10 g peanut flour (5 g peanut protein) and the Open OFC to 8 g peanut protein in natural food form at week 160.
Passing a blinded OFC is defined in [Section 3.3.1](#).
Passing an Open OFC is defined in Section 6.4.3.
2. Transient Desensitization Endpoint
This is the change in proportion of participants who pass the blinded OFC to 10 g peanut flour (5 g peanut protein) at week 134 and week 160.
Passing a blinded OFC is defined in [Section 3.3.1](#).
3. Highest Tolerated Cumulative Dose Endpoint
The highest tolerated cumulative dose of peanut protein during the blinded OFCs will also be collected and analyzed.

Safety:

1. The incidence of all adverse events.
2. Rates of withdrawal from OIT or placebo.

Mechanistic:

Changes in the following markers of immune mediation:

1. Secreted cytokines
2. Anti-peanut IgE, IgG, IgG4 and secretory IgA
3. Epitope arrays
4. IgE-facilitated, CD23-dependent allergen binding to B cells
5. Serum, stools, and saliva assays
6. PBMC expression of transcription factors and cytokines relevant to food allergy

7. CD4+ CD25+ FoxP3+ Tregs
8. DNA-HLA genotyping
9. Peanut-specific T cells
10. Ara h 1 and Ara h 2 reactive T cells
11. Th2A Subset Analysis Basophil activation
12. B cells

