6.2.2 Blinding

Blinding will be maintained for all study participants through the time of the final blinded 10 g peanut flour (5 g peanut protein) OFC, which will occur 26 weeks after cessation of OIT at the end of the study (week 160).

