Open Oral Food Challenge of week 160

An OpFC will be conducted for all participants who pass a 5g blinded OFC at week 160. During an OpFC, the participant must ingest a meal size portion (approximately 8 grams of peanut protein) of the food in its natural form (e.g., 2 tablespoons peanut butter) in an open setting in which all of the involved parties are aware of the identity of the food to make sure that it is tolerated.

The OpFC will be conducted 2 hours after passing a 5g blinded OFC. The peanut-containing food should be consumed during a 120 minutes maximum (30-60 minute preferred) time period at the participant's own pace (i.e., not in a stepwise or graded fashion). If the participant passes the OpFC,

the participant should be observed for a minimum of 2 hours or longer as indicated by the participant's status.

If the participant has negative reaction during OpFC but could not consume the full amount of open challenge material, a repeat OpFC may be scheduled within 14 days to determine the outcome. The investigator should discuss the case with the NIAID medical monitor and protocol chairs before scheduling a repeat OpFC.

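### Tolerance, the endpoint that sets N=144, requires passing both week-160 challenges in Section 3.3.2 but is analysed as the blinded OFC alone in Section 9.2.3.1

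*Combined protocol and SAP*

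**What the plan says.** Section 3.3.2 gives the tolerance endpoint as "The proportion of participants who pass both the blinded OFC to 10 g peanut flour (5 g peanut protein) and the Open OFC". The open part uses an 8 g portion, and both challenges fall at week 160. The section adds: "Passing an Open OFC is defined in Section 6.4.3". The synopsis gives the same two-part definition.

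Section 9.2.3.1, under the same endpoint name, says: "This is the proportion of participants who pass the blinded OFC to 10 g peanut flour (5 g peanut protein) at week 160". It mentions no open challenge and does not refer back to Section 3.3.2. It takes its methods from Sections 9.2.1 and 9.2.2. The failure rule in Section 9.2.2 names only an evaluable blinded OFC, and so does the per-protocol sample for the secondary endpoint in Section 9.1.

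The open challenge depends on the blinded one. Section 6.4.3 states: "An OpFC will be conducted for all participants who pass a 5g blinded OFC at week 160".

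Section 1.3 says that assessing tolerance "is a key study goal". Section 9.3 sizes the trial on tolerance, with completer rates of 0.40 and 0.15, 15% dropout counted as failure, 2:1 allocation and a two-sided 0.05 Pearson chi-squared test, giving 96 + 48 = 144 for 80% power. It does not say which challenge or challenges those rates describe.

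**The concern.** The two definitions are both current text and nothing in the documents reconciles them. Because only blinded passers go on to the open challenge, passing both is a subset of passing the blinded OFC, so the endpoint in Section 9 is equal or easier to meet. The two differ for any child who passes the blinded OFC and does not pass the open challenge: not tolerant under Section 3.3.2, tolerant under Section 9.2.3.1.

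The reported tolerance rate could therefore answer a different question from the stated endpoint. If the choice is left open, it could be made after results are known. It is also unclear which definition the 80% power supports.

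**Working it through.** **Where each section stands**

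| Place | Tolerance rests on |
|---|---|
| Synopsis | blinded and open challenge |
| Section 3.3.2 | blinded and open challenge |
| Section 9.1, secondary per-protocol sample | evaluable blinded OFC |
| Section 9.2.2, failure rule carried to tolerance | evaluable blinded OFC |
| Section 9.2.3.1 | blinded OFC |
| Section 9.3, rates 0.40 and 0.15 | not stated; dropout and return bullets name the week-160 blinded OFC |

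**The plan's own figure.** As-analysed rates: 0.40 × 0.85 = 0.34 and 0.15 × 0.85 = 0.1275. With n1 = 96, n2 = 48 and pooled rate p = (96 × 0.34 + 48 × 0.1275)/144 = 0.2692:

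power = Φ{[(p1 − p2) − 1.96 √(p(1−p)(1/n1 + 1/n2))] / √(p1(1−p1)/n1 + p2(1−p2)/n2)}

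= Φ{[0.2125 − 1.96 × 0.0784]/0.0682} = Φ(0.862) = 80.6%.

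At N=141 (94 + 47) power is 79.7%, so 144 is the smallest 2:1 total that reaches 80%. The plan's figure reproduces. Exact enumeration of the same test gives 81.6%.

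**How many children could change status.** Expected blinded passers, if the rates are blinded-only: 0.34 × 96 = 32.6 on OIT and 0.1275 × 48 = 6.1 on placebo. The documents give no open-challenge failure rate. I assume a fraction f of blinded passers fails it, the same in both arms, from 5% to 20%. That moves 1.6 to 6.5 children on OIT and 0.3 to 1.2 on placebo.

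**Reading A: 0.40 and 0.15 are blinded-only.** Pass-both rates are 0.34(1 − f) and 0.1275(1 − f).

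| f | OIT vs placebo | Power for passing both | Exact |
|---|---|---|---|
| 5% | 0.323 vs 0.121 | 77.5% | 78.7% |
| 10% | 0.306 vs 0.115 | 74.2% | 75.7% |
| 20% | 0.272 vs 0.102 | 66.9% | 68.6% |

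The point at which power drops below 80% depends on the method. By the normal approximation it is about f = 1%. By exact enumeration power is still 80.5% at 2% and is 79.9% at 3%.

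**Reading B: 0.40 and 0.15 already mean passing both.** Pass-both power stays at 80.6%. The blinded-only analysis as written would use 0.34/(1 − f) and 0.1275/(1 − f), with power 83.5%, 86.4% or 91.9% at the same three values of f.

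**Effect on the test result.** Uncorrected Pearson chi-squared at the planned counts (reading A): 33/96 vs 6/48, p = 0.005. With 20% failing in each arm (33 × 0.8 = 26.4; 6 × 0.8 = 4.8): 26/96 vs 5/48, chi-squared 5.26, p = 0.022. The result remains significant.

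These figures use the chi-squared test of Section 9.3. The planned analysis is a logistic model adjusted for site, peanut-specific IgE and age.

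**The case against.** **Section 9 is consistent with itself.** The sizing section ties dropout and return to the week-160 blinded OFC, and Section 9.2.3.1 uses the blinded OFC too, so sizing and analysis may both be blinded-only. This is a fair inference and the likelier reading. It remains an inference, because no sentence defines the rates, and it leaves the conflict with Section 3.3.2 in place.

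**The blinded-only endpoint is cleaner.** In the open challenge "all of the involved parties are aware of the identity of the food". On timing, the plan says: "The OpFC will be conducted 2 hours after passing a 5g blinded OFC". On masking it says: "Blinding will be maintained for all study participants through the time of the final blinded 10 g peanut flour" OFC, and promises nothing beyond that. This stands. As an illustration, suppose both arms pass the blinded OFC at 0.1275 and only placebo passers then fail the open challenge, at 10% or 20%. Comparing 0.1275 with 0.11475 or 0.102, the two-sided 5% test rejects about 5.2% or 6.5% of the time. That is a reason to report the blinded-only result alongside. It does not justify two definitions under one name.

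**A SAP may settle it.** Sections 9.2.1 and 9.2.4 leave subgroup, sensitivity and imputation details to a SAP. They do not defer the endpoint definition, and no text available here resolves it. It is therefore not established that children will be misclassified in practice, only that the text as written would do so.

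**Stronger readings.** A reader might infer that the trial is underpowered for tolerance. The documents do not support this: it needs reading A and a failure rate that they do not give. A reader might also hold placebo at 6/48 and remove OIT passers until significance is lost, which happens at 25/96 (p = 0.062). That requires 8 of 33 OIT passers and no placebo passer to fail. With one placebo failure, 25/96 vs 5/48 gives p = 0.030. Finally, a reader might think an open challenge left unfinished without a reaction has no scoring rule. Section 6.4.3 requires the portion to be eaten and allows a repeat, and Section 9.3 scores absent evaluable endpoint data as not tolerant, so this is largely settled and needs only confirmation.

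**Conclusion.** The contradiction holds: one named endpoint has two definitions in current text, and the one in the analysis section would count as tolerant a child who reacts to the open challenge. It should be fixed, but it is not critical. Tolerance is a secondary endpoint, the primary endpoint is unaffected, and N=144 is correct on its stated inputs.

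Its size depends on what 0.40 and 0.15 mean. Under reading A, and assuming equal open-challenge failure of 5% to 20% in both arms, pass-both power lies between 77.5% and 66.9%, or 78.7% and 68.6% exact. Under reading B nothing is lost. In neither case do the planned counts lose significance over that range with failures in both arms.

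**What to change.** Before unblinding:

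1. Use one definition throughout. Section 9.2.3.1 should follow the stated endpoint in Section 3.3.2 (pass both), with the blinded-OFC-only result reported as a supportive analysis because the open challenge is not blinded.
2. Align the secondary per-protocol wording in Section 9.1 with that definition, and confirm that the Section 9.3 rule on absent evaluable endpoint data covers the open challenge as well as the blinded OFC.
3. State in Section 9.3 which definition 0.40 and 0.15 describe. If blinded-only, restate the pass-both power under a stated failure assumption and leave N unchanged. If pass-both, the 80% stands.

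The reverse choice, blinded-only as the main analysis with pass-both as supportive, would also remove the conflict, but it would mean changing the endpoint stated in the synopsis and Section 3.3.2.

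The cost is a protocol or SAP amendment with the reviews in Section 9.4. It needs no new patients, visits or data, since the open challenge is already scheduled for every week-160 blinded passer. The downsides are a possibly less favourable stated power and an openly assessed component in the between-arm test, which the supportive analysis lets a reader check.

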The current study investigates long term tolerance by randomly assigning allergic subjects to peanut OIT or to placebo. After a dose escalation phase, subjects receive maintenance oral immunotherapy for an extended period. At the end of that period an assessment for peanut allergy is carried out. Then OIT or placebo is stopped, and subjects are observed during an avoidance phase. Participation will conclude with a final assessment for peanut allergy after the avoidance phase. This approach entails several design decisions, which can be justified by results of prior studies or regarded as assumptions.

The age of potential participants was chosen with the aim of finding a group whose immune system is more likely to be modified by OIT. Older children tend to have higher IgE levels and may be less likely to undergo desensitization successfully and to develop tolerance. Other entry criteria such as skin test wheal size and peanut-specific IgE level were chosen to ensure that participants have strong evidence of established peanut allergy. These objective measures are considered more important for study entry than clinical history which is less reliable.

Reactivity on an oral food challenge is part of the eligibility for the trial. While we expect children to react at different levels of peanut in an initial OFC, this level is not known to predict accurately the likelihood of desensitization or development of tolerance. Therefore stratification based on this level is not applied in this study. Children with asthma beyond a specified level of severity are excluded for safety considerations. Presence of a sibling in a subject's household with peanut allergy will not be considered an exclusion because we judge the risk of exposure to the investigational product is small and can be managed by families.

The protocol specifies minimum and target doses that must be achieved for the initial dose escalation, build-up and maintenance phases. The minimum dose for initial dose escalation is chosen based on findings in previous studies^{15,16} that such doses are tolerated in most subjects and allow continuation to the build-up phase.

The minimum maintenance dose for oral immunotherapy is unknown. In the current trial we propose a minimum maintenance dose less than the dose specified for an initial challenge that confirms peanut

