4. SELECTION AND WITHDRAWAL OF PARTICIPANTS

4.1 INCLUSION CRITERIA

Patients must meet *all* of the following criteria to be eligible for this study:

1. Age 12 months to less than 48 months, either gender.
2. Clinical history of peanut allergy or avoidance of peanut without ever having eaten peanut.
3. Serum IgE to peanut of ≥ 5 kUA/L determined by UniCAP™.
4. Wheal ≥ 3 mm on skin prick test to peanut extract compared to a negative control.
5. A clinical reaction as defined in [Section 6.4.3](#) at or below ingestion of 1 g peanut flour (500 mg peanut protein) during screening blinded OFC.
6. Written informed consent from parent/guardian.

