6.4.3 Oral Food Challenges (500mg, 5g and Open Food Challenge)

All OFCs conducted in the study are double blind and placebo controlled and will be performed so that neither the participant, nor the participant's caregiver, nor the physician knows which challenge contains the peanut or the placebo. The 500 mg OFC results will be unblinded in order to determine eligibility for the study since the participant must have a clinical reaction to this OFC to begin dosing. The results of the 500 mg OFC will be made available to study staff in order to determine eligibility.

Oral food challenges will be undertaken under direct medical supervision in a clinical research center or food challenge area with emergency medications and staff immediately available and will follow established study procedures.

Prior to a blinded OFC, participants will be off antihistamines for an appropriate length of time (5 half-lives of the antihistamine that is being used) and participants will be assessed for an exacerbation of asthma as determined by active wheezing and for a current flare in atopic dermatitis ([Section 6.7.2](#)).

Participants judged by the investigator to be at significant risk of severe reaction will have an intravenous line placed prior to the blinded OFC. Such participants would include those with a history of life-threatening anaphylaxis to any food, or a reaction to any food which caused dehydration and required intravenous fluid resuscitation.

A uniform approach for food challenges will be used. The blinded OFC will consist of 1 g or 10 g of peanut flour (500 mg or 5 g of the peanut protein) or placebo flour in gradually increasing doses at 15-30 minute intervals.

Although these minimum standards have been used safely in the past, the investigator may use clinical judgment to increase the intervals between doses or repeat lower doses, if there is a concern that a reaction may be developing. For the 500 mg blinded OFC, the set of doses will be comprised of the following: 1%, 4%, 10%, 20%, 20%, 20%, 25%. For the 5 g blinded OFC, the set of doses will be comprised of the following: 0.1%, 1%, 4%, 10%, 20%, 20%, 20%, 25%. Though many published challenges begin with 5% initial doses, the minimum dose for this study was chosen to be a lower dose according to additional recent recommendations and consensus³².

If conducted in a single day, at least 2 hours must separate the last dose of the first set of doses from the first dose of the second set.

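### The between-arm tolerated-dose analyses do not specify adjustment for the dose tolerated at the screening challenge

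*Combined protocol and SAP*

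**What the plan says.** Section 9.2.3.1, item 3, states: "The highest tolerated dose of peanut protein during each blinded OFC will be analyzed within and between both placebo and peanut OIT groups". It adds that "the highest dose of peanut protein tolerated for each subject will be analyzed as a continuous outcome", and it ties the method to the rest of the plan with "Each of these analyses will be performed in a similar manner as all other endpoint analyses". The between-arm model is given only as an illustration: "a multivariate linear model could be used to test for desensitization at 134 weeks and tolerance at 160 weeks". Parametric or non-parametric methods are left open, and no covariates are listed.

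The analyses it points back to are those of the primary and tolerance endpoints. Section 9.2.2 defines the first as a "multivariate logistic regression model with site, peanut specific IgE, and age as covariates in the model", and the tolerance endpoint uses the same methods. No other covariate is named for any efficacy model.

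The screening challenge is an entry requirement. Section 4.1 asks for a clinical reaction "at or below ingestion of 1 g peanut flour (500 mg peanut protein) during screening blinded OFC". Appendix 1 places that challenge at visit -1 and randomization at visit 0.

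Section 1.3 is the only place that discusses the prognostic value of the screening level. It says that the level is not established as an accurate predictor of desensitization or tolerance, and concludes: "Therefore stratification based on this level is not applied in this study". It does not mention adjustment in the analysis.

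**The concern.** The screening challenge measures the outcome itself, before treatment, in every eligible child. It is the natural first candidate for a covariate in a between-arm comparison of tolerated dose. Read as written, the plan carries over three covariates chosen for pass/fail endpoints and does not mention this one.

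Randomization is stratified by site only (Section 6.2.1), so nothing in the design balances the starting threshold. With 48 placebo children planned, a chance difference in starting threshold can move the estimated dose difference in either direction, and a model without the baseline value leaves that variation in the error term. The week-160 comparison has most to gain, because there the expected effect is moderate and the sample was sized with little to spare.

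**Working it through.** **1. The baseline value.** Section 6.4.3 gives the 500 mg challenge in percentage steps: "the set of doses will be comprised of the following: 1%, 4%, 10%, 20%, 20%, 20%, 25". Cumulating these and multiplying by 5 mg per percent gives 5, 25, 75, 175, 275, 375 and 500 mg. A child who reacts at one step has tolerated the total up to the step before. Eligible children therefore have a tolerated cumulative dose of 0, 5, 25, 75, 175, 275 or 375 mg, which is seven nominal levels. They are nominal because the investigator may repeat lower doses.

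**2. The plan's own figure.** Section 9.3 sizes the trial on the binary tolerance endpoint with 0.34 versus 0.1275, 2:1 allocation, two-sided 0.05 and 80% power.
- Pooled proportion: (2 × 0.34 + 0.1275)/3 = 0.2692.
- Placebo n = [1.96 × √(1.5 × 0.2692 × 0.7308) + 0.8416 × √(0.1275 × 0.8725 + 0.34 × 0.66/2)]² / 0.2125² = 47.4, rounded up to 48.
- Total: 48 + 96 = 144, which reproduces the plan. Power at 96 and 48 is 0.806.

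This figure does not depend on the present point. The plan states no power for the dose endpoint.

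**3. Chance imbalance.** The standard error of a baseline difference is √(1/96 + 1/48) = 0.177 SD. The 95% range is 1.96 × 0.177, or about ±0.35 SD.

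**4. Precision.** Let r be the correlation of baseline with follow-up dose after site, IgE and age are accounted for. The documents give no value, so a range is assumed. Residual variance is multiplied by 1 − r². For an effect that has 80% power without the covariate, power becomes Φ(2.80/√(1 − r²) − 1.96), and the equivalent total sample is 144/(1 − r²).

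| Assumed r | Variance reduction | SE reduction | Power | Equivalent N |
|---|---|---|---|---|
| 0 | 0% | 0% | 80.0% | 144 |
| 0.2 | 4% | 2.0% | 81.6% | 150 |
| 0.3 | 9% | 4.6% | 83.6% | 158 |
| 0.5 | 25% | 13.4% | 89.9% | 192 |

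**5. Simulation on the protocol's dose steps.** From the plan: 96 and 48 children; completer pass rates of 0.40 and 0.15 at week 160, and 0.90 and 0.15 at week 134; 15% dropout. Assumed: log10 threshold SD of 0.8, baseline spread evenly over the seven levels, and dropouts set to 0 mg. The models contained treatment with or without log10(baseline + 1), and no other covariates.

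Week 160, outcome in mg, 800 simulated trials per row:

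| Latent correlation | Correlation on mg scale | Power unadjusted | Power adjusted |
|---|---|---|---|
| 0 | 0.00 | 0.92 | 0.92 |
| 0.2 | 0.14 | 0.91 | 0.91 |
| 0.4 | 0.27 | 0.91 | 0.94 |
| 0.6 | 0.41 | 0.90 | 0.95 |

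At week 134, with 200 trials per setting, power in mg was 1.00 with and without the covariate.

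With the week-160 outcome on a log10(dose + 1) scale, power rose less: from 0.56 to 0.57 at latent 0.4, and from 0.55 to 0.59 at latent 0.6.

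**The case against.** Several points on the other side stand.

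- **The plan does not rule the covariate out.** The linear model is only an example, and the covariates reach this endpoint through the words about a similar manner. A reader might infer that the plan has chosen an analysis that excludes baseline dose. The text supports only that adjustment is not specified.
- **The comparison is not biased.** A reader might also infer that the unadjusted result would be invalid. Randomization protects it, and only precision and chance imbalance are affected.
- **Section 1.3 bears on the benefit.** Its doubt about prediction concerns the same states that the dose endpoint is meant to describe, so it suggests a modest gain. It does not settle the matter: its conclusion is limited to stratification, and a weak predictor of passing or failing can still explain variance in a continuous dose.
- **The larger gains are upper scenarios.** Site, IgE and age may already carry part of the information. Baseline is confined to 0 to 375 mg, and imputed failures dilute the correlation. At week 134 the expected effect is large and most treated completers are expected to reach the ceiling.

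Two replies to the point carry less weight. Item 3 refers to every blinded OFC, which read literally includes screening, but the uses it then names are week 134, week 160 and the change between them. Summarizing the screening dose by arm would not be adjusting for it. Section 9.2.1 leaves subgroup and sensitivity analyses to the SAP, but it does not say this of the main covariates, and the supplied text has no fuller list.

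**Conclusion.** The point holds as a minor improvement to one secondary endpoint. The plan does not specify adjustment for a pre-randomization measure of the outcome that every eligible child has, and its remark about prediction is not a reason against adjusting.

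The size depends on an assumed partial correlation. Residual variance falls by about 4% at 0.2, 9% at 0.3 and 25% at 0.5, and there is no gain at zero. On the protocol's dose steps, and under the stated assumptions, week-160 power changed by nothing at a latent correlation of 0.2, by about 3 points at 0.4 and by about 5 points at 0.6. There was no gain in mg at week 134. The primary analysis, the binary tolerance analysis and the sample size of 144 are unaffected.

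**What to change.** Before unblinding, state in the SAP that the week-134 and week-160 between-arm analyses of highest tolerated cumulative dose include site, peanut-specific IgE, age and the highest tolerated cumulative dose at the screening blinded OFC. Enter the last as ranks or as log(dose + a stated offset), since 0 mg is a possible value and its log is undefined. If a non-parametric method is used instead, name one that can carry these covariates, such as a rank analysis of covariance.

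No new data are needed, because the value is collected at screening. The statistical cost is one degree of freedom. The administrative cost is a change of SAP wording. If the covariate set is treated as a principal feature of the plan, Section 9.4 requires an amendment with the reviews listed there.
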